7.4 Intra-Procedural Assessments

During the Surfacer System procedure, the following data will be collected:

- Continuous ECG monitoring
- Contrast angiography (venography) to confirm occlusions.
- Fluoroscopy will be performed to confirm catheter tip position (catheter tip position must be visible on fluoro).
- Cone beam CT, intracardial echo, or other advanced imaging guidance to verify placement. Investigator must be able to clearly identify the level of occlusion. With Type IV occlusions, the Investigator must be able to definitively identify the remnant of SVC; if this cannot be accomplished by angiography, the operator should not proceed without advanced imaging guidance such as cone beam CT or intracardiac echo. Advanced imaging should also be utilized for some Type III TCVO lesions characterized by unusually tortuous vessels or otherwise challenging anatomy.
- AP and LAT chest x ray or cine-fluoroscopy will be performed post procedure to check the correct placement and position of the CVA Catheter tip, rule out pleuro-pulmonary damage (pneumothorax, hemothorax, etc.), and to detect pleural fluid and mediastinal widening.
- TTE (optional, only if cardiac events)
- Study Device Performance
- Adverse Events
- Protocol Deviations

7.5 Discharge/Post Procedure Assessments

Subjects will be carefully monitored with follow-up at hospital discharge and 7-days post procedure. At hospital discharge, the following assessments will be conducted and documented:

- Physical exam including vital signs
- Medications (antithrombotic and cardiovascular)
- Clinical laboratory tests including coagulation profile (APTT, PT, INR), CRP, LDH, ASAT, ALAT, fibrinogen, D-dimer
- AP and LAT chest x ray or cine-fluoroscopy, ideally assessed immediately after the index procedure is complete. If the Investigator determines that additional imaging is clinically indicated at the time of discharge (same day or next day discharge), a chest x-ray may be obtained.
- TTE (optional, only if symptomatic cardiac events)
- Adverse Events

- Protocol Deviations

At 7 Days (+ 7) post procedure, the following assessments will be conducted and documented. Although a generous visit window has been provided to allow for clinic visit scheduling, these assessments are to occur on Day 7 post procedure, or as soon as possible thereafter:

- Physical exam including vital signs
- Medications (antithrombotic and cardiovascular)
- Adverse Events
- Protocol Deviations

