1.3 Schedule of Assessments

STUDY ASSESSMENTS WILL OCCUR AS FOLLOWS:

Assessments/Interval	Screening	Baseline	Intra-Procedural	Hospital Discharge	7 Days (+7) Post Procedure ⁷
Informed Consent	X				
Study Eligibility	X				
Medical History/Demographics	X				
Physical Exam including Vital Signs		X		X	X
TCVO Lesion Type Classification		X			
Procedural Complication Assessment			X	X	X
Study Device Performance			X		
Medications (Antithrombotic & Cardiovascular)		X		X	X
Clinical Laboratory Tests¹					
Pregnancy Test ²	X ²				
Creatinine		X			
Coagulation Profile (APTT/PT/INR)		X		X	
CRP		X		X	
LDH/ASAT/ALAT		X		X	
Fibrinogen/D-dimer		X		X	
Exams and Tests³					
AP and LAT Chest X-Ray or cine-fluoroscopy		X ⁴	X	X ⁵	
Ultrasound or Venous Duplex Venography		X			
ECG 12-lead		X			
TTE			Only If Cardiac Events	Only If Cardiac Events	
Contrast Angiography			X		
Fluoroscopy			X		
Cone Beam CT/cardiac echo/advanced imaging modalities ⁶			X		
Adverse Events			X	X	X
Protocol Deviations		X	X	X	X

¹ Laboratory tests must be completed no more than 72 hours prior to the procedure.

² Pregnancy test is not required if patient is male or of non child bearing potential.

³ Ultrasound or Venous Duplex Venography must be completed no more than 7 days prior to the Screening Visit. Other Screening/Baseline tests must be completed no more than 30 days prior to the Procedure.

⁴ AP and LAT chest X-ray or cine fluoroscopy will be performed prior to the index procedure to define the pattern of occlusions, to rule out acute thrombosis, and to detect pleural fluid and mediastinal widening.

⁵ Post-procedural AP and LAT chest X-ray or cine fluoroscopy will be performed, ideally assessed immediately after the index procedure is complete, to check the correct placement and position of the CVA Catheter tip, rule out pleuro-pulmonary damage (pneumothorax, hemothorax, etc.), and to detect pleural fluid and mediastinal widening. If the Investigator determines that additional imaging is clinically indicated at the time of discharge (same day or next day discharge), a chest x-ray may be obtained.

⁶Cone Beam CT, cardiac echo, or similar advanced imaging modalities to be performed in subjects with Type IV TCVO lesions, and Type III TCVO lesions suspected to be characterized by unusually tortuous vessels or otherwise challenging anatomy.

⁷A +7 day visit window has been provided to allow for outpatient clinic scheduling. However - this visit is to occur on Day 7, or as soon as possible thereafter.

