6.4.2 Primary Safety Endpoints

- Acute device safety, defined as the absence of procedural complications (hemopericardium, hemothorax, pneumothorax, blood transfusion, resuscitation, emergency post-procedural intervention, transfer to an intensive care unit, and death) at discharge and 7 days post procedure.
- Overall device and procedure related anticipated adverse events compared to historical safety data from CV placement procedures.

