15.0 APPENDIX A

DEFINITIONS OF POTENTIAL RISKS

- **Pain** - Acute discomfort conveyed to the brain by sensory neurons associated with a symptom or disease.
- **Infection**— An infection is invasion and multiplication of microorganisms in body tissues accompanied by pain, fever, drainage and/or leukocytosis that is treated by anti-microbial agents (non-prophylactic).
- **Bleeding** – overt bleeding either associated with a drop in the hemoglobin level of at least 3.0 g/dL or requiring transfusion of two or three units of whole blood/RBC and does not meet criteria of life threatening or disabling bleeding.
- **Adverse Tissue Reaction; Allergic Reaction** - Localized or systemic hypersensitivity to contrast media, anesthesia or other medications used characterized by rash, nausea, vomiting, itching, shortness of breath, vasovagal reaction or anaphylaxis. The specific allergen should be reported if known.
- **Cardiovascular Sequela, including perforation, tamponade, spasm or effusion; Perforation-** Perforation detected by the clinical site requiring additional treatment including efforts to seal the perforation. **Tamponade** - The term cardiac tamponade will be used to describe a pericardial effusion sufficiently to cause circulatory compromise and require drainage. Any cardiac tamponade is considered serious and procedure related. **Spasm** - A transient constriction of the lumen of one or more vessels due to contraction of vascular smooth muscle **effusion – Pericardial effusion** is defined as a new fluid collection within the pericardial space, with or without cardiac tamponade, as identified by echocardiography or CT imaging.
- **Lymphatic System Sequelae** - Lymphatic system sequelae is recognized by the new occurrence of lymph drainage at the procedure site, or a new accumulation of lymphatic fluid (lymphocele) near the procedure site.

- **Pulmonary Sequelae including: pneumothorax and pulmonary embolism – Pneumothorax** - abnormal collection of air in the pleural space that causes an uncoupling of the lung from the chest wall. **Pulmonary embolism** is defined as obstruction of one or more pulmonary arteries by dislodged venous thrombi or foreign materials.
- **Vascular sequelae including vasospasm, vessel perforation, dissection, or aneurysm;**

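### Appendix A classifies bleeding by a haemoglobin drop that no scheduled test measures, and excludes the gravest bleeds without a higher bleeding grade to receive them

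*Combined protocol and SAP*

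**What the plan says.** **Laboratory panels.** Section 7.5 lists for discharge: "Clinical laboratory tests including coagulation profile (APTT, PT, INR), CRP, LDH, ASAT, ALAT, fibrinogen, D-dimer". Section 7.2 repeats that list for screening and baseline. The Schedule of Assessments (1.3) adds a pregnancy test and a baseline creatinine, and its first footnote sets the timing: "Laboratory tests must be completed no more than 72 hours prior to the procedure". Haemoglobin or a blood count appears in none of the three places. No laboratory test is scheduled at Day 7.

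**Definition.** Appendix A describes Bleeding as "overt bleeding either associated with a drop in the hemoglobin level of at least 3.0 g/dL". The alternative criterion is that two or three units were transfused. A bleed qualifies only if it "does not meet criteria of life threatening or disabling bleeding". Appendix A does not say what makes a bleed life-threatening or disabling, and it has no second bleeding term.

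**Use of the definition.** Section 5.5 lists Bleeding among the potential risks and sends the reader to Appendix A for definitions. Section 9.1.2 takes the anticipated adverse events from Section 5.5 and the Instructions for Use (IFU). Section 6.4.2 makes device- and procedure-related anticipated events, set against historical data, the second primary safety endpoint. The first is the absence of listed complications: "hemopericardium, hemothorax, pneumothorax, blood transfusion, resuscitation, emergency post-procedural intervention", ICU transfer and death.

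**The concern.** A drop in haemoglobin needs a value before and a value after, and the protocol schedules neither. An overt bleed that is not transfused enters the Bleeding term only through that drop, so whether it is classified depends on local testing practice, across up to 10 sites. At the other end, the definition sets aside the gravest bleeds and supplies no higher grade to take them. It reads like the middle tier of a graded scale whose top tier is absent.

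Bleeding is not a marginal risk here. Both complications counted in Table 4 for earlier inside-out experience were haematomas. The procedure brings a needle wire out through the skin and then passes a 16F introducer over it (Sections 3.1 and 3.3). If bleeds fall out of the anticipated-event count, a primary safety comparison with historical rates looks better than it should.

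**Working it through.** **1. Where each kind of overt bleed goes, as the text stands**

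| Overt bleed | Appendix A Bleeding term | First primary safety endpoint |
|---|---|---|
| Not transfused, drop of 3.0 g/dL or more, not life-threatening or disabling | Yes, but only if haemoglobin was measured outside the schedule | Only if another listed event occurs |
| One unit, not life-threatening or disabling | Only by the haemoglobin criterion | Yes |
| Two or three units, not life-threatening or disabling | Yes | Yes |
| Four or more units, not life-threatening or disabling | Only by the haemoglobin criterion | Yes |
| Life-threatening or disabling | No | Where transfusion, resuscitation, emergency intervention, ICU transfer, death or another listed event occurs |

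Scheduled haemoglobin values: 0 of the 2 needed. Only the third row can be classified as Bleeding from what the protocol itself requires to be recorded.

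The table takes the exclusion to qualify both criteria. If it were attached to the transfusion criterion alone, a life-threatening bleed could enter through haemoglobin, which is again unscheduled.

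**2. Other routes into the second endpoint.** Section 5.5 and Appendix A also list cardiac perforation, tamponade, pericardial effusion, vessel perforation and death. A life-threatening or disabling bleed that meets one of these terms is an anticipated event under that name. One that meets none of them is anticipated only if the IFU lists it, and the IFU is not among the documents.

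**3. The plan's own precision figures.** With n = 30 and x events, the exact 95% limits are the 0.025 quantile of Beta(x, n − x + 1) and the 0.975 quantile of Beta(x + 1, n − x). For 27/30 this gives 73.5% to 97.9%, and for 15/30 it gives 31.3% to 68.7%. Both agree with Section 8.2.2.

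**4. What one subject is worth.** 1/30 = 3.3 percentage points. By the same method:

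| Counted | Rate | Exact 95% CI |
|---|---|---|
| 0/30 | 0% | 0 to 11.6% |
| 1/30 | 3.3% | 0.1 to 17.2% |
| 2/30 | 6.7% | 0.8 to 22.1% |
| 3/30 | 10.0% | 2.1 to 26.5% |

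Counting none instead of one lowers the upper limit from 17.2% to 11.6%. For scale, the overall complication rate in Table 4 is 2/136 = 1.47%, less than one subject in this study.

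**5. Illustration under assumed rates.** The documents give neither an expected bleeding rate p nor the share s of bleeds that would be counted under the term. The chance that none of 30 subjects is counted is (1 − p·s)^30.

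- s = 1: p = 5% gives 0.95^30 = 21.5%; p = 10% gives 0.90^30 = 4.2%.
- s = 0.5: p = 5% gives 0.975^30 = 46.8%; p = 10% gives 0.95^30 = 21.5%.

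These show sensitivity to the assumptions. They are not an estimate of the undercount.

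**The case against.** The case on the other side is substantial, and most of it stands as a limit on the point.

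- **Detection.** The term requires overt bleeding, so a silent laboratory drop would not count even if measured. Overt bleeds are looked for by complication assessment, physical examination and adverse event collection. A reader might infer that bleeds go unseen; the documents support only that a bleed already seen may be unclassifiable.
- **First primary safety endpoint.** A reader might infer that both primary safety endpoints are under-counted. The first lists transfusion with no unit limit, as well as hemothorax, hemopericardium and the main severe consequences. The fault lies in the second.
- **Large transfusions.** It is tempting to say that four or more units can never count as Bleeding. They can, by the haemoglobin criterion, if the bleed is not life-threatening or disabling and a site tested.
- **Safety reporting.** A life-threatening event is serious under Section 9.1.3. If device-associated and not previously identified in severity, it is an unanticipated adverse device effect, reported to the monitoring committee and FDA within 10 working days (9.1.5). Excluded bleeds would not vanish from the safety record.
- **Open wording.** The panel lists are worded as inclusive, Section 5.5 is not exhaustive, and the IFU may name further bleeding events.
- **Disagreement between endpoints.** Transfusion in the first endpoint does not require a bleed. The two endpoints measure different things, and a patient counted in one only is not in itself an error.
- **Purpose.** The study is unpowered (8.2.2), and Section 8.3.8 plans no hypothesis test on adverse event rates.

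None of this supplies a paired haemoglobin, criteria for the exclusion, or a bleeding grade above it.

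**Conclusion.** The point holds for the second primary safety endpoint. Haemoglobin is a classifying criterion that the protocol does not schedule. Life-threatening or disabling bleeds are removed from the term by undefined criteria and count as anticipated only if they meet another listed term or the IFU names them. The likely direction is too few anticipated bleeding events, which would flatter the device.

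The size cannot be computed: it depends on the bleeding rate, on unscheduled local testing, on overlap with other terms and on the IFU. The documents do not support reading this as a proven bias in the overall safety result, or as a loss of the worst bleeds from all reporting. In a descriptive 30-subject study this should be fixed, but it is not critical to the study's validity. It is better done before enrolment, because a haemoglobin that was not measured cannot be recovered later.

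**What to change.** 1. Add haemoglobin to the Baseline and Hospital Discharge laboratory rows in 1.3 and to the lists in 7.2 and 7.5, using blood already drawn. The existing 72-hour rule would then govern the baseline value.
2. For counting only, reconcile the Appendix A term so that every overt bleed at or above its existing lower threshold, including life-threatening or disabling bleeding, is one anticipated bleeding event graded by severity. State the criteria for the top grade, and check the term against the IFU.
3. Do not record every transfusion as Bleeding. A transfusion may have another cause, and one unit alone is below the term's transfusion threshold. Report transfusion separately under the first primary safety endpoint.

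The cost is one analyte at two existing draws, two case report form fields and a wording change. The reported bleeding rate may rise. A bleed that starts after discharge would still depend on unscheduled testing, since no blood is drawn at Day 7; the sponsor should either accept and state this or add a draw.

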7.6 Subject Withdrawal

Subject study participation is voluntary and subjects may withdraw from the study at any time without penalty or compromise to their medical care. Additionally, a subject may be withdrawn from the study at any time at the discretion of the Principal Investigator, if the Principal Investigator believes that continuation in the study could result in unnecessary risks or jeopardize the subject's health and welfare.

The reason for withdrawal will be documented at the time of study withdrawal. All study data collected up to the point of withdrawal will be included in the data analysis and maintained as part of the study documentation.

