7.3 Subject Enrollment

A subject will be considered “enrolled” in the study when they have completed informed consent, are qualified per all study screening requirements and component of the investigational study device is inserted into the subject.

Once a subject has been exposed to the study device, even if the Investigator is unable to complete the Surfacer treatment, the study subject will be considered part of the intent-to-treat population and will be followed up to 7 days post-procedure, or until any adverse events are resolved.

See Section 8.0 for description of analysis populations and statistical considerations.

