7.8 Study Discontinuation

The study may be discontinued at any time by BVT or applicable regulatory agency. If the study is discontinued before study activities have been completed, all study data collected up to the point of discontinuation shall remain the property of the BVT and will be subject to all applicable patient and data privacy requirements.

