9.0 SAFETY

Safety monitoring will be performed by the Principal Investigator during the conduct of this study. An Adverse Events (AE) will be recorded and assessed from the time of enrolment through study completion or early withdrawal. All AEs will be followed by the Principal Investigator until resolution or stabilization.

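### Section 9.0 ends recording of new adverse events at early withdrawal, so a device-exposed subject withdrawn under Section 7.6 can have a listed complication before Day 7 that is never recorded, contrary to Section 7.3

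*Combined protocol and SAP*

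**What the plan says.** Four parts of the protocol bear on this.

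- **Enrolment and follow-up (Section 7.3).** A subject counts as enrolled only after consent, qualification and the point at which a "component of the investigational study device is inserted into the subject". Once exposed, the subject belongs to the intent-to-treat population and "will be followed up to 7 days post-procedure, or until any adverse events are resolved", even if the treatment could not be completed.
- **Withdrawal (Section 7.6).** Apart from the subject's own right to leave, "a subject may be withdrawn from the study at any time at the discretion of the Principal Investigator", if the investigator believes that "continuation in the study could result in unnecessary risks or jeopardize the subject's health and welfare". On data, the section says: "All study data collected up to the point of withdrawal will be included in the data analysis". It is silent on safety contact after withdrawal.
- **Adverse event recording (Section 9.0).** Events are "recorded and assessed from the time of enrolment through study completion or early withdrawal". The next sentence adds: "All AEs will be followed by the Principal Investigator until resolution or stabilization".
- **Endpoint and analysis (Sections 8.2.1, 8.3.5 and 8.3.9).** The first primary safety endpoint is freedom from eight listed complications, ICU transfer and death among them, at discharge and at 7 days. The primary analysis is in the intent-to-treat population. Endpoints are analysed with and without missing data, with last observation carried forward (LOCF) as the main imputation method.

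**The concern.** Exposure to this device is a single procedure, and the device is removed once the catheter is in place. After that, the only study activities left are the discharge and Day 7 assessments. Withdrawing a subject at that stage does not reduce device exposure; it ends observation.

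Sections 7.3 and 9.0 give a site different instructions for that subject. Under 7.3 the site keeps following to Day 7. Under 9.0, read with 7.6, it stops recording new events on the day of withdrawal. Nothing says which governs. Because the ground for investigator withdrawal concerns risk and health, the resulting missingness may be related to outcome. What is at stake is complete ascertainment of a primary safety endpoint in a study of 30 subjects, where a single event is visible in the result.

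**Working it through.** **1. The plan's own precision figures.** Section 8.2.2 uses exact Clopper-Pearson 95% limits with n = 30. For x events, the lower limit is the 0.025 quantile of Beta(x, n − x + 1) and the upper limit is the 0.975 quantile of Beta(x + 1, n − x). This gives 31.3% to 68.7% for 15/30 and 73.5% to 97.9% for 27/30. Both match the plan, so the same formula is used below.

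**2. Who can be affected.** Enrolment occurs at insertion of a component. Any withdrawal of an enrolled subject is therefore a withdrawal of an exposed subject, to whom the follow-up in 7.3 applies.

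**3. Which events can be lost.** Three cases need to be separated:

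- A listed complication before withdrawal is already recorded, and the subject already fails the endpoint. Nothing is lost.
- An adverse event open at withdrawal must still be followed to resolution or stabilization under the second sentence of 9.0. It is not dropped.
- A new listed complication after withdrawal and before Day 7, in a subject who had none at withdrawal, falls outside the recording window in 9.0 but inside the follow-up in 7.3. This is the gap.

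**4. What the analysis does with the third case.** The subject's last recorded status is no complication. LOCF carries that forward to Day 7. The analysis without missing data drops the subject. Neither shows the event.

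**5. Illustration.** The documents give no withdrawal rate. Assume that 1 or 2 of 30 subjects are withdrawn event-free, that each then has an unrecorded listed complication, and that no other subject has one.

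| Lost events (assumed) | Complete Day 7 ascertainment, or worst case | LOCF | Withdrawn subjects excluded |
|---|---|---|---|
| 1 | 1/30 = 3.3% (0.1 to 17.2%) | 0/30 = 0% (0 to 11.6%) | 0/29 = 0% (0 to 11.9%) |
| 2 | 2/30 = 6.7% (0.8 to 22.1%) | 0/30 = 0% (0 to 11.6%) | 0/28 = 0% (0 to 12.3%) |

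For zero events the upper limit is 1 − 0.025^(1/n); with n = 30 this is 11.6%. Under LOCF the upper limit is understated by 17.2 − 11.6 = 5.6 percentage points for one lost event and by 22.1 − 11.6 = 10.5 points for two.

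**The case against.** The strongest reply is that the gap is narrow and may never matter. An adverse event is defined broadly in 9.1.1, so a subject who is deteriorating at withdrawal already has a recordable event, which 9.0 requires the investigator to follow. The condition in 7.6 is that continuing in the study carries risk. When only observation remains, that condition should seldom be met. A general follow-up duty alongside a withdrawal clause is ordinary drafting. No performance threshold is stated that the shift would cross, and 8.3.9 allows additional imputation methods.

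Most of this stands and sets the limits of the point. It does not remove the conflict over new events. Further imputation can bound the effect of a missing Day 7 status but cannot recover an event that was not collected, and 8.3.9 makes it conditional on being judged appropriate.

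A reader might also infer more than the text supports:

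- *That 7.6 itself stops adverse event recording or forbids later data.* It does not. Its data sentence is an inclusion rule; the end of recording is set in 9.0.
- *That the withdrawn subjects are those most likely to have events.* A health-based ground makes this plausible, but nothing in the documents shows it.
- *That treated subjects are dropped if the study stops.* Section 7.8 begins "If the study is discontinued before study activities have been completed, all study data collected up to the point of discontinuation", but its main clause concerns ownership and privacy of the data. Section 9.1.5 allows termination of only the parts of the study that present the risk. Neither tells sites to end follow-up of subjects already treated.

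**Conclusion.** The point holds in limited form. Sections 7.3 and 9.0, the latter read with 7.6, conflict on whether new adverse events are recorded to Day 7 in an exposed subject whom the investigator withdraws. If 9.0 governs, a new listed complication can be missed, and both planned treatments of missing data would leave it out of the count. The error would favour the device.

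The size depends on an assumption, because no withdrawal rate is given: one or two lost events in 30 would turn an observed 3.3% or 6.7% into 0%. Each lost event requires both a withdrawal without a listed complication and a new listed complication before Day 7 in the same subject. The precision figures in Section 8.2.2 are correct and are not disputed. The change is worth making because it protects a primary endpoint at very little cost.

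**What to change.** Reconcile Sections 7.3, 7.6 and 9.0.

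- **Section 9.0:** replace *or early withdrawal* with *or withdrawal of consent for further data collection*.
- **Section 7.6:** state that withdrawal by the investigator does not end safety data collection for a device-exposed subject. Day 7 vital status and the eight listed complications are then collected by visit, telephone or chart review, unless the subject withdraws consent for this.
- **Sections 8.3.5 and 8.3.9:** for the primary safety endpoint, do not let LOCF score a missing Day 7 status as event-free without a worst-case sensitivity analysis beside it, in which each such subject counts as having an event.

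The cost is a wording change and a telephone or chart check for the few subjects affected. No visits or subjects are added.
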